### **5.6.1 Discontinuation of Study Therapy after CR**

Discontinuation of treatment may be considered for subjects who have attained a confirmed CR that have been treated for at least 24 weeks or PR for 48 weeks with pembrolizumab and had at least two treatments with pembrolizumab beyond the date when the initial response was declared. Subjects who then experience radiographic disease progression may be eligible for up to one year of additional treatment with pembrolizumab via the Second Course Phase at the discretion of the investigator if no cancer treatment was administered since the last dose of pembrolizumab, the subject meets the safety parameters listed in the Inclusion/Exclusion criteria. Subjects will resume therapy at the same dose and schedule at the time of initial discontinuation. Additional details are provided in Section 7.1.5.5.

### **5.7 Subject Replacement Strategy**

### **5.8 Clinical Criteria for Early Trial Termination**

Early trial termination will be the result of the criteria specified below:

1. Quality or quantity of data recording is inaccurate or incomplete
2. Poor adherence to protocol and regulatory requirements
3. Incidence or severity of adverse drug reaction in this or other studies indicates a potential health hazard to subjects
4. Plans to modify or discontinue the development of the study drug

In the event of Merck decision to no longer supply study drug, ample notification will be provided so that appropriate adjustments to subject treatment can be made.

## 6.0 TRIAL FLOW CHART

### 6.1 Study Flow Chart

Trial Period:	Treatment Cycles									End of Treatment		
Treatment Cycle/Title:	Screening	1	2	3	4	To be repeated beyond 8 cycles				Discontinue 	Safety Follow-up 	Long term Follow up
Scheduling Window (Days):	-28	± 3 d	± 3d	± 3d	± 3d	± 3d	± 3d	± 3d	± 3d	At time of Discontinue	30 days post discontinue	Q12 weeks from Safety F/U visit
Informed Consent	X											
Inclusion/Exclusion Criteria	X											
Demographics and Medical History	X											
Prior and Concomitant Medication Review	X	X	X	X	X	X	X	X	X	X	X	
Trial Treatment Administration		X	X	X	X	X	X	X	X			
Post-study anticancer therapy status											X	X
Survival Status												X
Review Adverse Events	X	X	X	X	X	X	X	X	X	X	X	
Full Physical Examination	X	X	X	X	X	X	X	X	X 	X	X	
Vital Signs and Weight	X	X	X	X	X	X	X	X	X	X.	X.	
ECOG Performance Status	X	X	X	X	X	X	X	X	X	X	X	
Pregnancy Test – Urine or Serum	X											
PT/INR and aPTT 	X											

IRB ID: Pro20170001392  
Approval Date: 2/22/2023  
Expiration Date: 5/10/2023

Trial Period:		Treatment Cycles								End of Treatment		
Treatment Cycle/Title:	Screening	1	2	3	4	To be repeated beyond 8 cycles				Discontinue 	Safety Follow-up 	Long term Follow up
						5	6	7	8			
Scheduling Window (Days):	-28	± 3 d	± 3d	± 3d	± 3d	± 3d	± 3d	± 3d	± 3d	At time of Discontinue	30 days post discontinue	Q12 weeks from Safety F/U visit
CBC with Differential 	X	X	X	X	X	X	X	X	X	X	X	
CMP, LDH, Uric Acid, Phos, Mg, D. Bili (if t.bili > ULN) 	X	X	X	X	X	X	X	X	X	X	X	
Urinalysis	X											
T3, FT4 and TSH 	X	X	X	X	X		X		X		X	
Tumor Imaging 	X				X			X		X		
Tumor Markers	X				X			X		X		
PD-L1 analysis	X 											
Archival or Newly Obtained Tissue Collection 	X		X 							X 		
Correlative Studies Blood Collection (PBMC and serum)	X		X 							X 		
Circulating Cell-free tumor DNA (Plasma)	X			X		X		X 		X		

After 24 weeks, PE to be performed once every six weeks.

 All screening labs should be performed within 10 days of treatment initiation (refer to inclusion criteria #7, Table 1). CBCD, CMP to be performed prior to each treatment. See Table 5 for complete list of chemistries. After cycle 4, thyroid function tests to be performed every six weeks.

IRB ID: Pro20170001392  
Approval Date: 2/22/2023  
Expiration Date: 5/10/2023

Tumor imaging (CT chest/abdomen/pelvis preferred; MRI may be used in select instances if felt to be clinically appropriate by investigator) to be performed after every three cycles until commencement of eight cycles, when imaging will be performed after every four cycles (Prior to Cycles 4 and 7, then prior to Cycles 11, 15, 19, etc). Tumor imaging to be completed within 7 days of next scheduled cycle. Patients who enroll with known prior disease will require MRI brain repeat imaging every 12 weeks.

 Archived tumor tissue is required for enrollment of all patients (20 unstained slides preferred, minimum of 15 required). Newly obtained biopsy may occur if inadequate tissue is available. Optional biopsies will be obtained after 4 weeks and at mandatory biopsies at progression. PBMCs will be drawn at baseline, Cycle 2, and at progression. Correlative tumor and blood may be collected within a +/- 7 day window.

Tumor imaging and RECIST measurements will continue past end of treatment until time of progression.

Plasma samples for circulating cell-free tumor DNA will be collected every 6 weeks of treatment, whenever scheduled times coincide, at the time of PBMC or standard of care blood draws. Samples may be collected within a +/- 7 day window.

Refer to the MISP Sample Handling Manual for collection and shipping instructions.

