Mandatory tumor assessments include collection of archived or fresh tumor at baseline and a biopsy of tumor upon progression. Fresh tumor biopsies or archived tumor tissue will be collected at baseline as well as peripheral blood mononuclear cell (PBMC) samples. Patients will be treated with pembrolizumab dosed at 200 mg intravenous infusion every three weeks (1 cycle = 21 days). Patients will be evaluated for response by RECIST 1.1 and iRECIST criteria after every 9 weeks (3 cycles) of treatment until cycle 8, then subsequently after every 12 weeks (4 cycles) of treatment. PBMCs (tumor optional) will be sampled to assess treatment effect on the immune response at the following time points: baseline and after week 4 of pembrolizumab. Mandatory submission of PBMC tumor biopsies at progression will occur provided that the biopsy of the progressing tumor does not impose significant risk in the opinion of the investigator. Plasma samples for analysis of cell-free DNA will also be collected prior to initiation of treatment, and every 6 weeks of treatment. The above design and assessments are depicted in the schema below.

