**Table 3. Dose Modification Guidelines for Drug-Related Adverse Events**

Toxicity	Hold Treatment For Grade	Timing for Restarting Treatment	Discontinue Subject
Diarrhea/ Colitis	2-3	Toxicity resolves to Grade 0-1.	Toxicity does not resolve within 12 weeks of last dose or inability to reduce corticosteroid to 10 mg or less of prednisone or equivalent per day within 12 weeks.
	4	Permanently discontinue	Permanently discontinue
AST, ALT, or Increased Bilirubin	2	Toxicity resolves to Grade 0-1	Toxicity does not resolve within 12 weeks of last dose.
	3-4	Permanently discontinue (see exception below) 	Permanently discontinue
Type 1 diabetes mellitus (if new onset) or Hyperglycemia	T1DM or 3-4	Hold pembrolizumab for new onset Type 1 diabetes mellitus or Grade 3-4 hyperglycemia associated with evidence of beta cell failure.	Resume pembrolizumab when patients are clinically and metabolically stable.
Hypophysitis	2-3	Toxicity resolves to Grade 0-1	Toxicity does not resolve within 12 weeks of last dose or inability to reduce corticosteroid to 10 mg or less of prednisone or equivalent per day within 12 weeks.
	4	Permanently discontinue	Permanently discontinue
Hyperthyroidism	3	Toxicity resolves to Grade 0-1	Toxicity does not resolve within 12 weeks of last dose or inability to reduce corticosteroid to 10 mg or less of prednisone or equivalent per day within 12 weeks.
	4	Permanently discontinue	Permanently discontinue
Hypothyroidism	2-4	Therapy with pembrolizumab can be continued while treatment for the thyroid disorder is instituted	Therapy with pembrolizumab can be continued while treatment for the thyroid disorder is instituted.
Infusion Reaction	3-4	Permanently discontinue	Permanently discontinue
Pneumonitis	2	Toxicity resolves to Grade 0-1	Toxicity does not resolve within 12 weeks of last dose or inability to reduce corticosteroid to 10 mg or less of prednisone or equivalent per day within 12 weeks.
	3-4	Permanently discontinue	Permanently discontinue
Renal Failure or Nephritis	2	Toxicity resolves to Grade 0-1	Toxicity does not resolve within 12 weeks of last dose or inability to reduce corticosteroid to 10 mg or less of prednisone or equivalent per day within 12 weeks.
	3-4	Permanently discontinue	Permanently discontinue

Toxicity	Hold Treatment For Grade	Timing for Restarting Treatment	Discontinue Subject

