### **7.1.2.5 Tumor Imaging and Assessment of Disease**

All tumor assessments will be performed according to the Trial Flow Chart (Section 6.0). If a patient discontinues treatment for any reason other than progression, tumor assessments will be done every 12 weeks ( $\pm$  14 days) for duration of study disease monitoring of 24 months unless after cycle 8 in which case they will be performed every 16 weeks ( $\pm$  14 days).

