##### **7.1.5.2 Treatment Period**

The treatment period consists of 8 treatment cycles, which repeat from cycle 5 if treatment continues beyond cycle 8. At each cycle throughout the treatment period, the following are to be performed and/or assessed for each patient: a review of prior and concomitant medications,

administration of trial treatment, survival status, a review of adverse events, a full physical examination (after 24 weeks, a physical exam will be performed once every 6 weeks), the patient's vital signs and weight, the patient's ECOG performance status, CBC with differential, and CMP (both to be performed prior to each treatment). T3, FT4, and TSH will be measured at cycle 1 through cycle 4 (after cycle 4, these thyroid function tests are to be performed every 6 weeks). Tumor imaging (CT chest/abdomen/pelvis preferred; MRI may be used in select instances if felt to be clinically appropriate by investigator) is to be performed after every 3 cycles until commencement of 8 cycles, after which time imaging will be performed after every 4 cycles. An MRI of the brain will be required every 12 weeks for patients who enroll with known prior disease. Optional biopsies will be obtained after 4 weeks and at mandatory biopsies at progression. PBMCs will be drawn after 4 weeks of therapy, and at progression. Correlative tumor and blood may be collected with a +/- 7 day window.

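### On-treatment scans are tied to cycle numbers, so one maximal dose hold can move the week-9 scan to week 18 or the week-18 scan to week 27, and the timing of progression assessment depends on tolerability

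*Combined protocol and SAP*

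**What the plan says.** - Section 6.1, footnote 3: imaging is "to be performed after every three cycles until commencement of eight cycles, when imaging will be performed after every four cycles". The scans are placed by cycle number, "Prior to Cycles 4 and 7, then prior to Cycles 11, 15, 19, etc", and the window is also set against dosing: "Tumor imaging to be completed within 7 days of next scheduled cycle".
- Section 7.1.5.2 repeats the cycle count: "performed after every 3 cycles until commencement of 8 cycles, after which time imaging will be performed after every 4 cycles".
- Section 2.1 gives weeks and cycles as one quantity, "after every 9 weeks (3 cycles) of treatment until cycle 8, then subsequently after every 12 weeks (4 cycles) of treatment", with dosing "every three weeks (1 cycle = 21 days".
- Section 7.1.2.5 makes the flow chart the governing schedule: "All tumor assessments will be performed according to the Trial Flow Chart (Section 6.0".
- Table 3 discontinues the patient, for most toxicities that allow a hold, only when "Toxicity does not resolve within 12 weeks of last dose". The text after Table 3 also permits interruptions unrelated to study therapy, with return within 3 weeks.
- Section 7.1.2.5.6 dates progression, and response, to the scan that first showed it.

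No section says what happens to the scan schedule while dosing is on hold.

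**The concern.** Three cycles take 9 weeks only if every dose is on time. When a dose is held, the next cycle has not arrived, so on the flow chart's wording the scan attached to it is not yet due. Because progression is dated to a scan, PFS dates and first-response dates in held patients then depend partly on how well the drug was tolerated.

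The secondary objective concerns response durability (immune-related PFS) against historical information, and section 8.0 plans a 6-month PFS rate. Section 8.0 has no rule for late scans and no sensitivity analysis for them. With no control arm, uneven assessment timing has nothing to cancel against.

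Other imaging in the protocol already runs on calendar time: brain MRI every 12 weeks where required, confirmatory scans at 4 to 6 weeks, and follow-up scans after stopping without progression. A patient who stops permanently before cycle 8 is scanned every 12 weeks, whereas one on a temporary hold may go 18.

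**Working it through.** **Inputs.** Cycle of 21 days (section 2.1); scans before Cycles 4, 7, 11 and 15 (section 6.1, footnote 3); hold limit of 12 weeks from last dose (Table 3); 6-month PFS of 35% (section 8.0), with 6 months taken as 26 weeks.

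**The plan's own figure.** 3 × 21 days = 9 weeks and 4 × 21 days = 12 weeks. Uninterrupted dosing puts the scans at weeks 9, 18, 30 and 42, so the equivalence in section 2.1 is reproduced for a patient with no delay.

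**One maximal hold.** The dose gap becomes 12 weeks instead of 3, a delay of d = 9 weeks.
- After Cycle 3 (week 6): Cycle 4 falls at 6 + 12 = week 18 and Cycle 7 at 18 + 9 = week 27. Scans: 18, 27, 39, 51. Holds after Cycle 1 or 2 give the same dates.
- After Cycle 6 (week 15): Cycle 7 falls at 15 + 12 = week 27. Scans: 9, 27, 39, 51. Holds after Cycle 4 or 5 give the same dates.

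Either way there is an 18-week stretch without a scheduled scan (baseline to 18, or 9 to 27). A 3-week delay moves the scans to 12 and 21, or to 9 and 21.

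**Model (assumption).** Exponential time to progression, no deaths, scans on the cycle dates. Hazard = −ln(0.35)/26 = 0.0404 per week, giving S(9) = 0.695, S(18) = 0.483, S(21) = 0.428, S(24) = 0.379 and S(26) = 0.350.

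**Measured 6-month PFS.** This is S at the last scan on or before week 26. On the intended schedule it is S(18) = 48.3%, because the next scan is at week 30.

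| Delay d | Delay before Cycle 4 | Delay between Cycles 4 and 7 |
|---|---|---|
| 3 weeks | S(21) − S(18) = −5.5 points | −5.5 points |
| 6 weeks | S(24) − S(18) = −10.4 points | −10.4 points |
| 8 weeks | S(26) − S(18) = −13.3 points | −13.3 points |
| 9 weeks | S(18) − S(18) = 0 | S(9) − S(18) = +21.2 points |

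For d up to 8, the second scan falls at week 18 + d, still no later than week 26. It picks up progression that the intended schedule would not record until week 30. Just above 8 weeks, a delay before Cycle 4 gives at most S(17) − S(18) = 0.503 − 0.483 = +2.0 points.

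Separate delays can add up. Six weeks plus three, both between Cycles 4 and 7, also reach week 27. If the three weeks fall before Cycle 4 instead, the scans are at weeks 12 and 27, and the rise is S(12) − S(18) = 0.616 − 0.483 = 13.3 points.

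**Mean recorded progression time.** Mean = Σ t_k × [S(t_(k−1)) − S(t_k)] over the scan dates t_k, continuing every 12 weeks. The intended schedule gives 30.4 weeks.
- Delay between Cycles 4 and 7: +0.36 weeks at d = 3 and +1.65 at d = 9.
- Delay before Cycle 4: +0.56 weeks at d = 3 and +2.49 at d = 9.

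The range is therefore about 0.4 to 2.5 weeks later.

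**The case against.** Section 2.1 puts weeks first, and footnote 3 refers to the next scheduled cycle, so a site could keep scanning by the calendar. That is possible, but the cycle list in footnote 3 is explicit and section 7.1.2.5 makes the flow chart govern. If sites read it differently, they will scan on different schedules, which the same wording change cures.

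There are partial safeguards. Section 7.1 allows unscheduled procedures, symptomatic clinical deterioration counts as confirmed progression (section 7.1.2.5.4), one hepatic situation calls for imaging (Table 3, note 1), and discontinuation has its own scan. A hold decided at the Cycle 4 or Cycle 7 visit may follow a scan already done, and the 7-day window lets a scan for a week-27 cycle fall at week 26. These reduce the problem, but none is a general rule for scans during a hold.

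The strongest objection concerns consequence, and it stands. A reader might infer that later scans inflate 6-month PFS in general, and might multiply 21 points by an assumed 10–20% of held patients to get a cohort rise of about 2–4 points. The documents do not support this. They give no hold rate; the 21-point case needs a delay of more than 8 of the possible 9 weeks, after an on-time first scan; many Grade 3–4 events in Table 3 lead to permanent discontinuation instead of a long hold; and shorter delays lower the measured rate. A biased historical comparison cannot be inferred either, since the historical scan schedules are not in the documents.

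**Conclusion.** The concern holds as a matter of assessment timing. Scans follow cycle numbers, most holds may run to 12 weeks from last dose, and one maximal hold moves the week-9 scan to week 18 or the week-18 scan to week 27.

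Recorded PFS and response dates therefore depend partly on tolerability. On average, recorded progression is modestly later in held patients (about 0.4 to 2.5 weeks for delays of 3 to 9 weeks). The 6-month PFS rate has no single direction of error: it falls by up to about 13 points for a patient delayed by up to 8 weeks before Cycle 7, and rises by up to about 21 points only after a near-maximal or cumulative delay. The cohort effect cannot be sized without a hold rate.

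These sizes rest on the exponential model, the 35% rate, no deaths, and scans on the cycle dates. PFS is a secondary endpoint. The primary endpoint, response rate, is little affected because it uses the best response up to progression and has no fixed time point. This is a cheap improvement and no threat to the trial's main result.

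**What to change.** In section 2.1, section 6.1 footnote 3 and section 7.1.5.2, define on-treatment scans by weeks from Cycle 1 Day 1 at the protocol's own intervals: weeks 9, 18, 30 and 42, then every 12 weeks, each within a 7-day window, regardless of dose holds or delays. Remove the link to cycle numbers. No dosing or hold rule changes.

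The cost is wording in one amendment. Patients dosed on time keep the same visits; a patient on hold occasionally attends for a scan without an infusion. Scans not done at the time cannot be recovered at analysis, so the change has to be prospective.

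This makes assessment times uniform. It does not cure the separate fixed gap between weeks 18 and 30 around the 6-month landmark, where in the model above even the intended schedule reads 48.3% against 35%.

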## **7.0 TRIAL PROCEDURES**

### **7.1 Trial Procedures**

The Trial Flow Chart - Section 6.0 summarizes the trial procedures to be performed at each visit. Individual trial procedures are described in detail below. It may be necessary to perform these procedures at unscheduled time points if deemed clinically necessary by the investigator. Furthermore, additional evaluations/testing may be deemed necessary by the Sponsor and/or Merck for reasons related to subject safety. In some cases, such evaluation/testing may be potentially sensitive in nature (e.g., HIV, Hepatitis C, etc.), and thus local regulations may require that additional informed consent be obtained from the subject. In these cases, such evaluations/testing will be performed in accordance with those regulations.

#### **7.1.1 Administrative Procedures**

##### **7.1.1.1 Informed Consent**

The Investigator must obtain documented consent from each potential subject prior to participating in a clinical trial.

###### **7.1.1.1.1 General Informed Consent**

Consent must be documented by the subject's dated signature or by the subject's legally acceptable representative's dated signature on a consent form along with the dated signature of the person conducting the consent discussion. A copy of the signed and dated consent form should be given to the subject before participation in the trial.

The initial informed consent form, any subsequent revised written informed consent form and any written information provided to the subject must receive the IRB/ERC's approval/favorable opinion in advance of use. The subject or his/her legally acceptable representative should be informed in a timely manner if new information becomes available that may be relevant to the subject's willingness to continue participation in the trial. The communication of this information will be provided and documented via a revised consent form or addendum to the original consent form that captures the subject's dated signature or by the subject's legally acceptable representative's dated signature.

Specifics about a trial and the trial population will be added to the consent form template at the protocol level. The informed consent will adhere to IRB/ERC requirements, applicable laws and regulations and Sponsor requirements.

###### **7.1.1.2 Inclusion/Exclusion Criteria**

All inclusion and exclusion criteria will be reviewed by the investigator or qualified designee to ensure that the subject qualifies for the trial.

### **7.1.1.3 Medical History**

A medical history will be obtained by the investigator or qualified designee. Medical history will include all active conditions, and any condition diagnosed within the prior 10 years that are considered to be clinically significant by the Investigator. Details regarding the disease for which the subject has enrolled in this study will be recorded separately and not listed as medical history.

### **7.1.1.4 Prior and Concomitant Medications Review**

#### **7.1.1.4.1 Prior Medications**

The investigator or qualified designee will review prior medication use, including any protocol-specified washout requirement, and record prior medication taken by the subject within 28 days before starting the trial. Treatment for the disease for which the subject has enrolled in this study will be recorded separately and not listed as a prior medication.

#### **7.1.1.4.2 Concomitant Medications**

The investigator or qualified designee will record medication, if any, taken by the subject during the trial. All medications related to reportable SAEs and ECIs should be recorded as defined in Section 7.2.

### **7.1.1.5 Disease Details and Treatments**

#### **7.1.1.5.1 Disease Details**

The investigator or qualified designee will obtain prior and current details regarding disease status.

#### **7.1.1.5.2 Prior Treatment Details**

The investigator or qualified designee will review all prior cancer treatments including systemic treatments, radiation and surgeries.

#### **7.1.1.5.3 Subsequent Anti-Cancer Therapy Status**

The investigator or qualified designee will review all new anti-neoplastic therapy initiated after the last dose of trial treatment. Once new anti-cancer therapy has been initiated the subject will move into survival follow-up.

### **7.1.1.6 Assignment of Screening Number**

The coordinating site will assign each patient a screening number.

### **7.1.1.7 Trial Compliance (Medication/Diet/Activity/Other)**

The investigator or qualified designee will review trial compliance regarding medication, contraception, scheduled assessments, other.

## **7.1.2 Clinical Procedures/Assessments**

All clinical procedures/assessments will be performed according to the Trial Flow Chart (Section 6.0).

